1.0 SCHEMA

[figure not shown]
2.0 Introduction and Background

2.1 Introduction and Background

The accurate detection and localization of cancers *in vivo* are critical to medical decisions and improved treatments. Unfortunately, limitations of contrast (reporter) agents, resolution, and restrictions of depth reduce the ability of most imaging methods to detect and localize multiple contrast agents simultaneously. Alternatively, optical-fluorescent imaging can simultaneously detect multiple biomarkers using fluorescently labeled peptides or antibodies as contrast agents; however, these approaches are restricted to superficial detection, as light scattering degrades the spatial resolution at increased penetration depths greater than 8 mm. Multispectral optoacoustic tomography (MSOT) is emerging as an alternative modality that is not restricted by many of the limitations of the imaging used in diagnosis and treatment of diseases¹. MSOT was initially developed for research, but has been adapted for clinical uses²⁻⁴ (see Table 1).

Optoacoustic imaging is based upon a “light-in, sound-out,” i.e. shining a light into the tissue and when the light hits the tissue, it can send a sound wave which we will capture using the MSOT device, approach through which absorption of near-infrared light (NIR) within biological tissues generates ultrasonic waves with much less scattering, longer range of detection, and higher accuracy compared with traditional optical imaging. The optoacoustic approach is unique, with increased optical contrast and signal-to-noise ratios¹. Optoacoustic imaging retains the advantages of optical imaging, including high specificity to identify functional and molecular processes in living organisms with high sensitivity. Most tissues are relatively transparent to NIR light in the range of 600 to 900 nm; therefore, use of NIR light excitation and ultrasound signals renders photon scattering irrelevant to image formation, enabling high-resolution images of the biological function of tumors and organs. Once the sound waves are generated, they obey the physical laws of sound transmission; the intensity of the sound increases with the number of molecules excited, but is reduced by distance and the extent of ultrasound diffraction due to different densities of tissue. In MSOT, multiple spectral components of NIR light are varied automatically to excite specific molecules, permitting accurate tomographic images to be constructed from the resulting ultrasonic signals. MSOT is also unique in its ability to detect multiple contrast agents simultaneously based upon differential spectral shape.

Changes in vasculature are often associated with both tumor development and progression, but microvascular changes occur below the resolution of common clinical imaging modalities. MSOT identifies microvasculature and tissue oxygenation by hemoglobin absorption of multiple wavelengths of light to generate high optoacoustic contrast^{1,4-6}.

Because oxy- and deoxy-hemoglobin each generate a unique optoacoustic signal, both oxy- and deoxy-hemoglobin can be observed simultaneously without the addition of exogenous contrast agents using MSOT (Figure 1). MSOT can distinguish between oxygenation states of hemoglobin, i.e. oxy-hemoglobin vs deoxy-hemoglobin, allowing visualization of differential blood saturation by oxygen within tissues, including the capability to differentiate between tumor and the surrounding tissue^{2,7} as well as inflammation associated with Crohn's disease³.

Imaging of tumors and cancer-related morphologic changes in tissues by MSOT is facilitated through exogenous contrast agents, including clinically approved optical dyes (e.g., isosulfan blue or indocyanine green)⁸, markers targeted to cell surface molecules, for example, EGFR¹¹, the tumor microenvironment (e.g., pH)⁹, and endogenous absorbers (i.e., oxyhemoglobin)^{2,10}. Use of MSOT in multiple tissue types and at varying depths, i.e., at least 5 cm^{3,8}, can provide functional real-time three-dimensional (3D) information at high spatial resolution *in vivo*¹. This ability will have a significant impact on clinical care in systemic diseases, including cancer involving multiple organs. The ability of MSOT to identify tumors indicates great potential for clinical applicability for solid tumors, such as melanoma, head and neck, breast, pancreatic, prostate, colon, and potentially, liver cancer.

2.2 Clinical Studies

MSOT has been used in research^{1,6,11,12} and clinical studies^{2,3,7,8} (including 6 clinical trials described in Table 1) and there has been no evidence of serious adverse events associated with the use of the device. Using a similar instrument in breast cancer, an optoacoustic imaging system from Seno Medical Instruments has received a CE mark in April 2014. Confirmatory studies for product approval of this particular device and specific indication have been started during the last years (with a focus on safety and performance). Presently, there has not been any association of phototoxicity associated with the use of MSOT in any clinical trial (Table 1).

Table 1 Clinical Trials using MSOT

Indication	Purpose of trial	Patients	References	Status
Peripheral atherosclerosis – healthy volunteers	The current project comprises a proof of principal study to test the technical feasibility of the use of Multispectral Optoacoustic Tomography (MSOT) in healthy volunteers for non-invasive measurements and imaging of perfusion and oxygenation in the lower legs. By measuring peripheral blood oxygenation and perfusion with a prototype handheld MSOT probe and comparing that to standard ultrasound imaging, pulse-oximetry and standard ankle-brachial index as a gold standard, the diagnostic accuracy and measurement ranges in physiologic conditions as determined by MSOT will be tested.	10 (The Netherlands)	NTR4125 http://www.trialregister.nl/trialreg/admin/rctview.asp?TC=4125	Published in Radiology
Limb ischemia, atherosclerosis	This study aims to investigate the feasibility and clinical performance of MSOT imaging of the feet in Peripheral Vascular (PVD) patients. Our main objective is to investigate and obtain new information about the state of arteries in PVD patients using MSOT. Our second objective is to investigate the use of MSOT compared to duplex ultrasound and standard diagnostic work-up (including Fontaine classification) in providing more information on microvascular perfusion and oxygenation in the extremities in relation to severity of the PVD. The patients will be imaged on both feet at particular landmarks, which include large arteries (arteria tibialis posterior and dorsalis pedis) and microvasculature (on each of the toes). The images will be compared to duplex ultrasound images of the large arteries, which are acquired as part of the standard of care, as well as other available diagnostic information, including the Fontaine classification.	24 (The Netherlands)	NTR4461 http://www.trialregister.nl/trialreg/admin/rctview.asp?TC=4461	Closed; Data analysis ongoing
Melanoma	This prospective study tests if photoacoustic tomography (PAT) and high-resolution ultrasound in combination with an indocyanine green injection is the first valid method to exactly assess the sentinel node status in melanoma patients in a non-invasive way and without exposing the patient to radioactivity. Therefore, preoperative, in vivo PAT results will be compared to the in vivo results based on standard diagnostics. Additionally, postoperative ex vivo PAT results followed by histological assessment will be compared.	40/120 (Germany)	DRKS00006329 http://www.drks.de/drks_web/navigate.do?navigationId=trial.HTML&TRIAL_ID=DRKS00006329 DRKS00005447 http://www.drks.de/drks_web/navigate.do?navigationId=trial.HTML&TRIAL_ID=DRKS00005447	First 20 patients: Published in Sci. Transl. Med. http://stm.sciencemag.org/content/7/317/317ra199 Next 60 patients: Data analysis
Crohn's disease/ Ulcerative colitis	The proposed study is designed as a pilot study to evaluate the usefulness of MSOT for the evaluation of disease activity in IBD patients. As current methods for the evaluation of intestinal inflammation in IBD have relevant restrictions, new, non-invasive, quantitative, and accurate modalities are urgently needed. In comparison to other techniques, MSOT provides relevant advantages such as non-invasive imaging, high spatial resolution (this is of special importance for the evaluation of the intestine, which can be only a	344 (Germany)	NCT02622139 https://clinicaltrials.gov/ct2/show/NCT02622139?term=MSOT&rank=1	Recruiting; First case study published in Gastroenterology in motion

	few millimeters thick), and highly sensitive detection of specific molecules such as total hemoglobin or oxy- /deoxygenated hemoglobin. These advantages suggest MSOT as an outstanding technique for evaluating disease activity in IBD.			
Breast Cancer	Evaluation of breast cancer based upon oxy- and deoxy-hemoglobin. MSOT provided high special resolution of breast tissue at centimeter depths.	Germany		Clinical Cancer Research
Alopecia	Dermal Papilla cells (DPCs) of hair follicle units (HFU) derived from balding and non-balding regions of the scalp have differences in terms of their genetic, morphologic and functional characteristics. One of the study goals is to evaluate the ability of a new technology called multi-spectral optoacoustic tomography (MSOT) to non-invasively image the structural information of hairs and surroundings.	20 (Singapore)	Not available	First case study submitted for publication
Basal cell carcinoma	The purpose of this research study is to evaluate if MSOT can accurately map non-melanoma carcinomas with the objective to determine lesion dimensions to aide in surgical removal. Two- and three-dimensional handheld MSOT probes are compared in terms of their performance in mapping the non-melanoma lesions.	Not available (Singapore)	Not available	First case study submitted for publication

3.0 Objectives

This IDE FDA approved study will involve the interaction with patients that are scheduled for routine standard of care surgery. It will be a single-arm study that is designed to provide safety information regarding the use of the Acuity MSOT device in the clinical setting and the ability of MSOT imaging data to correlate with clinical findings identified via pathology. We will initially study the safety data in 10 patients, and will expand the study with FDA approval to include 40 more patients after an interim analysis (refer to section 10.3 for more details).

3.1 Primary Objective(s)

- 3.1.1 To collect safety data on patients in whom MSOT was used to image tumor or lymph nodes
- 3.1.2 To evaluate skin temperature pre and post imaging (pre- and post-surgery) as part of the safety evaluation of MSOT

3.2 Secondary Objective(s)

- 3.2.1 To detect tumor or lymph node by MSOT before and after surgical removal
- 3.2.2 To determine tumor positivity based on tissue pathology and detection of oxy- and deoxy-hemoglobin using MSOT localization
- 3.2.3 To determine tumor volume by MSOT before and after surgical resection

4.0 Patient Selection

4.1 Inclusion Criteria

- 4.1.1 Patients with an identified solid tumor, i.e. breast (Stage I-IV), melanoma (Stage I-IV), HNSCC (Stage I-III), pancreatic (Stage I-III), ovarian (Stage I-IV) that is scheduled for surgical removal of the tumor and completed standard imaging prior to surgery
- 4.1.2 Have acceptable hematologic status [total hemoglobin (tHb) \geq 10 mg/dL]
- 4.1.3 Patients \geq 18 yrs of age
- 4.1.4 Patient provided a signed and dated informed consent
- 4.1.5 Willing to comply with study procedures and be available for the duration of the study
- 4.1.6 Ability to understand and the willingness to sign an IRB-approved informed consent document.

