4.2 Exclusion Criteria

- 4.2.1 Patients with central nervous system tumors
- 4.2.2 Patients with a tattoo over the surgical site
- 4.2.3 Pregnant women
- 4.2.4 Women who are breastfeeding
- 4.2.5 Systemic or local infection
- 4.2.6 Any systemic anomaly during the pre-op assessment preventing patient participation in the study
- 4.2.7 Any febrile illness that precludes or delays participation preoperatively
- 4.2.8 Anything that would put the participant at increased risk or preclude compliance with the study
- 4.2.9 Patients with Stage IV pancreatic cancer, Stage IV HNSCC are not surgical candidates and therefore excluded from this study

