6.2 Secondary Outcomes

- 6.2.1 Tumor positivity as based on standard clinical laboratory techniques and signal detection of oxy- and deoxy-hemoglobin using MSOT localization
- 6.2.2 Tumor volumes as estimated by MSOT and by standard clinical laboratory techniques
- 6.2.3 Identification of tumor and/or lymph nodes based upon either Isosulfan Blue or IC Green dye

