- ii. Identification of tumor and/or lymph nodes based upon either Isosulfan Blue or IC Green dye

3. Design information

a. General statistical considerations

This IDE FDA approved study will involve the interaction with patients that are scheduled for routine standard of care surgery. It will be a single-arm study that is designed to provide safety information regarding the use of the Acuity MSOT device in the clinical setting and the ability of MSOT imaging data to correlate with clinical findings identified via pathology.

b. Sample Size and Power

Study will initially accrue 10 patients for safety analysis regarding the use of the MSOT device pre- and post-surgery. If there are no grade III-V AEs observed in the patients as defined in CTCAE v5.0 per Section 8.2, we will submit an IDE supplement to request an enrollment expansion for an additional 40 patients, for a total of 50 patients. Up to an additional 55 patients will be accrued (to account for patient dropouts) to enroll 40 patients.

4. Study Populations

Inclusion and exclusion criteria are sometimes modified during the duration of the protocol. Before beginning analysis, the statistical team will review the criteria in the SAP to confirm it is up to date with the current criteria.

a. Inclusion Criteria

- i. Patients with an identified solid tumor, i.e. breast (Stage I-IV), melanoma (Stage I-IV), HNSCC (Stage I-III), pancreatic (Stage I-III), ovarian (Stage I-IV) that is scheduled for surgical removal of the tumor and completed standard imaging prior to surgery
- ii. Have acceptable hematologic status [total hemoglobin (tHb) \geq 10 mg/dL]
- iii. Patients \geq 18 yrs of age
- iv. Patient provided a signed and dated informed consent
- v. Willing to comply with study procedures and be available for the duration of the study
- vi. Ability to understand and the willingness to sign an IRB-approved informed consent document.

b. Exclusion Criteria

- i. Patients with central nervous system tumors
- ii. Patients with a tattoo over the surgical site
- iii. Pregnant women
- iv. Women who are breastfeeding
- v. Systemic or local infection
- vi. Any systemic anomaly during the pre-op assessment preventing patient participation in the study
- vii. Any febrile illness that precludes or delays participation preoperatively
- viii. Anything that would put the participant at increased risk or preclude compliance with the study

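### The hemoglobin eligibility limit is written in mg/dL in both documents, so the only numeric hematologic criterion excludes nobody if read literally; the unit needs confirming and correcting

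*Protocol*

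**What the plan says.** Protocol 4.1.2 lists among the inclusion criteria one that opens "Have acceptable hematologic status [total hemoglobin (tHb" and that reads, with its number and unit, "Have acceptable hematologic status [total hemoglobin (tHb) \geq 10 mg/dL". SAP section 4.a.ii carries the same criterion with the same number and unit. No other section of either document gives a hemoglobin limit in a different unit or amends this one.

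The exclusion criteria set no hemoglobin or anemia limit. Two general clauses could still reach an anemic patient. Protocol 4.2.6 excludes "Any systemic anomaly during the pre-op assessment preventing patient participation in the study", and 4.2.8 covers anything that raises the participant's risk or prevents compliance.

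SAP section 4 adds a check before analysis: "the statistical team will review the criteria in the SAP to confirm it is up to date with the current criteria".

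Hemoglobin is also part of what the device measures. Secondary outcome 6.2.1 is "Tumor positivity as based on standard clinical laboratory techniques and signal detection of oxy- and deoxy-hemoglobin using MSOT localization", and Appendix B records hemoglobin parameters from the MSOT images.

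**The concern.** An inclusion limit is an operative rule: under Protocol 5.2, eligibility has to be established before a Study ID is issued. A limit far below any value a patient could have does no screening. The number 10 beside this unit looks like a unit slip, but the documents do not say so, and the reader has to guess what was meant.

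Two things are at stake. The first is consistency: one person may apply the text as written and another may silently substitute a different unit, so eligibility depends on the reader. The second is verification: a monitor comparing a laboratory value with the written limit learns nothing, because every value passes. The SAP's check for agreement with the current criteria would not reveal the problem, since both documents carry the same unit.

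**Working it through.** The plan derives no figure here, so there is nothing to reproduce. The check is a unit conversion followed by a comparison.

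**Inputs**
- Written limit: 10 mg/dL (Protocol 4.1.2; SAP 4.a.ii).
- Conversion: 1 g = 1,000 mg.
- Patient hemoglobin: not given in the documents. I assume 2 to 18 g/dL, chosen wide enough to run from extreme anemia to high normal.

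**Step 1: the limit in g/dL.** 10 mg/dL ÷ 1,000 = 0.01 g/dL.

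**Step 2: the assumed range in the written unit.** Value in mg/dL = value in g/dL × 1,000. The ratio is that value divided by the limit of 10.

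| Assumed hemoglobin (g/dL) | In mg/dL | Ratio to written limit | Meets 4.1.2 as written |
|---|---|---|---|
| 2 | 2,000 | 200 | yes |
| 5 | 5,000 | 500 | yes |
| 8 | 8,000 | 800 | yes |
| 12 | 12,000 | 1,200 | yes |
| 18 | 18,000 | 1,800 | yes |

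**Step 3: sensitivity to the assumption.** The smallest ratio is 200. For the limit to exclude anyone, a patient's value would have to fall below 0.01 g/dL, which is one two-hundredth of the lowest value assumed. Any plausible range gives the same answer: applied literally, the criterion excludes 0% of patients.

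**Step 4: what the error touches.** The primary outcomes in Protocol 6.1 are adverse events and skin temperature. The sample size and interval bounds in 10.3 depend on the number of patients and the number of events. The detectable differences in 10.2 depend on the number of patients, alpha and power. The hemoglobin limit enters none of these.

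**The case against.** The strongest reply is practical. Staff who compare the number 10 with a laboratory report in g/dL would apply a limit that does bind, whatever the text says. The documents do not show how the criterion is applied, so the 0% describes the written rule and not necessarily the enrolled patients. That stands. It does not rescue the text, because the rule then in use would differ from the approved one and could vary between readers.

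A reader might infer several stronger things that the documents do not support.

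- *That patients lose their only protection on blood status before surgery.* They do not. Exclusions 4.2.6 and 4.2.8 allow exclusion on judgement, surgery is standard of care and already scheduled (4.1.1), and Protocol 7.1 has patients go through standard preparation for it. Criterion 4.1.2 is the only numeric hematologic criterion, not the only safeguard. The documents link no MSOT hazard to low hemoglobin.
- *That the limit protects the imaging signal, so the secondary outcomes are compromised.* Hemoglobin is a signal source, so an effect is possible. But the criterion is justified only as a matter of hematologic status, no section ties the limit to signal quality, and no size of effect can be derived.
- *That eligibility cannot be audited.* It can; everyone passes. The audit is uninformative, not impossible.
- *That the SAP's own safeguard fails.* The SAP sentence describes keeping its list of criteria current. It is not a patient-level eligibility check, so its only bearing is that agreement between the two documents is no evidence that the unit is right.

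**Conclusion.** The point holds as a unit error in an operative threshold: wrong as written, low severity. As stated in both documents the limit is 0.01 g/dL, and every patient in an assumed range of 2 to 18 g/dL exceeds it at least 200-fold. The range is my assumption, but the margin is wide enough that the conclusion does not depend on it. Taken literally, the criterion excludes nobody; taken as a slip, it is replaced by a limit the approved text does not contain. The documents do not show which reading was used, and no harm to patients or bias in any result is demonstrated. The primary outcomes, sample size, confidence intervals and stated power stand.

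**What to change.** The sponsor should confirm the intended limit and unit against the unit in which the laboratory reports hemoglobin, then correct Protocol 4.1.2 and SAP 4.a.ii in the same revision so that the two stay in agreement. No clinical limit is proposed here.

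The recorded screening values of patients already enrolled should then be re-checked against the confirmed limit. The two data forms appended to the protocol have no field for a screening hemoglobin value, so unless another study form holds it, the values would come from source laboratory records.

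The cost is one line in each document, the usual review of an amendment, and a record check on at most the planned 50 patients. No analysis has to change.

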4.2 Exclusion Criteria

- 4.2.1 Patients with central nervous system tumors
- 4.2.2 Patients with a tattoo over the surgical site
- 4.2.3 Pregnant women
- 4.2.4 Women who are breastfeeding
- 4.2.5 Systemic or local infection
- 4.2.6 Any systemic anomaly during the pre-op assessment preventing patient participation in the study
- 4.2.7 Any febrile illness that precludes or delays participation preoperatively
- 4.2.8 Anything that would put the participant at increased risk or preclude compliance with the study
- 4.2.9 Patients with Stage IV pancreatic cancer, Stage IV HNSCC are not surgical candidates and therefore excluded from this study

4.3 Inclusion of Women and Minorities

- Women and individuals of all races and ethnicities who meet the above-described eligibility criteria are eligible for this trial
- The study consent form will also be provided in Spanish for Spanish-speaking participants. Based on population estimates, we expect approximately 52% of participants to be women. Translating this to our expanded sample size estimate of 50, we plan to enroll at least 26 women. We plan to enroll at least 6% Native American, Hispanic/Latino, or African American (N=3). This would result in at least 6 patients of Fitzpatrick Skin Type I, 40 patients of Fitzpatrick Skin Type II-IV, and 4 patients of Fitzpatrick Skin Type V-VI. Because of the population distribution of our area we do not expect to accrue many individuals of Asian/Pacific Islander ancestry.

5.0 Subject Registration and Enrollment

5.1 Required protocol specific regulatory documents

This protocol, the Informed Consent document, any information to be given to the patient, and relevant supporting information must be submitted to the IRB by the Principal Investigator and reviewed and approved by the IRB before the study is activated.

